### 2.2 CLINICAL DATA

That CRF must be completed with all the following information:

- Age
- Gender
- Height

- Weight
- Ethnicity
- Superficial distance between jugulum and symphysis (surrogate of aortic length) – see above
- Waist circumference
- Smoking status
- Alcohol drinking
- Coffee or tea drinking
- Dyslipidemia (yes/no and indication on treatment)
- Diabetes (yes/no and indication on treatment)
- Diagnosis of hypertension (yes/no and indication on treatment)
- Family history of premature CV disease
- Medical history, with particular regard to previous and/or concurrent CV diseases
- Office blood pressure and heart rate obtained in the same treatment condition as ABPM (only one value can be input: it could be the average of more values or just a spot measurement)
- Left ventricular mass index (LVMI) at echocardiogram
- When available, diameter of the ascending aorta assessed by the echocardiogram
- Intima-media thickness (IMT) at carotid ultrasonography
- ECG (indication on left ventricular hypertrophy, Sokolow–Lyon and Cornell index)
- When available, ankle-brachial index
- Microalbuminuria (as mg/24h) or albumin-creatinine ratio (as mg/g) and serum creatinine (estimated glomerular filtration rate – eGFR will be calculated by the software according to the Cockcroft-Gault formula)
- When available, pulse wave velocity (PWV), augmentation index (AI) and central systolic blood pressure taken during the office visit with a validated device different from BPLab Vasotens (e.g. Sphygmocor or Complior)

Additionally, this information must be recorded at any visit:

- Drug treatments: explain that in case treatments are changed or replaced the Investigator must indicate dates and status. It is not necessary to add the drug again.
- Investigators must pay attention to record at any visit both new diseases and adverse events: the latter must be recorded in the “Events” section with start and end date and all the information needed to identify the event. Priority must be given to cardiovascular events, whereas other events must be placed under the label “Other” and a description must be entered.

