14.0 DATA MANAGEMENT

14.1 Electronic Case Report Form (e-CRF)

Data will be collected for each patient by an e-CRF located on a website. The e-CRF will allow the collection of the main demographic and clinical data including the patient's medical history and concomitant therapies. All data must accurately reflect the patients' view, or be an expression of their knowledge about their health.

The following data will be entered in the e-CRF, for each subject and visit:

- Age
- Gender
- Height
- Weight
- Ethnicity
- Superficial distance between jugulum and symphysis (surrogate of aortic length)
- Waist circumference
- Smoking status
- Alcohol drinking
- Coffee or tea drinking
- Dyslipidemia (yes/no and indication on treatment)
- Diabetes (yes/no and indication on treatment)
- Diagnosis of hypertension (yes/no and indication on treatment)
- Family history of premature CV disease
- Medical history, with particular regard to previous and/or concurrent CV diseases
- Office blood pressure and heart rate obtained in the same treatment condition as ABPM
- Left ventricular mass index (LVMI) at echocardiogram
- When available, diameter of the aorta (aortic annulus, root and sinotubular junction) and/or cardiac output, assessed by the echocardiogram
- Intima-media thickness (IMT) at carotid ultrasonography
- ECG (indication on left ventricular hypertrophy, Sokolow–Lyon and Cornell index)
- When available, ankle-brachial index

- Microalbuminuria and serum creatinine (calculation of estimated glomerular filtration rate - eGFR)
- When available, pulse wave velocity (PWV) augmentation index (AI) and central blood pressure taken during the office visit with a validated device different for BPLab Vasotens (e.g. Sphygmocor or Complior)

Access to the e-CRF will be granted through authentication with ID and password. The investigator will be responsible for the faithful transcription of the results of any laboratory or instrumental diagnostic tests. If changes have to be made to data, they will be overwritten with the correct ones. The system will keep record of the date and time of the corrections.

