### 3.1 EVALUATION OF CLINICAL CHARACTERISTICS

Evaluation and comparison of the main study parameters for the following groups:

- Males vs. females
- Young (<65 years) vs. old ( $\geq 65$  years)
- Age at risk:  $\geq 55$  years in males and age  $\geq 65$  years in females
- Ethnicity
- Smoking (smoker, no smoker, ex-smoker)
- Alcohol (yes vs. no)
- Coffee or tea (yes vs. no)
- Smoking or alcohol or coffee (yes vs. no)
- Family history for cardiovascular disease (yes vs. no)
- Previous cardiovascular diseases (yes vs. no)
- Any previous medical condition (yes vs. no)
- Arterial hypertension (untreated and treated)
- Antihypertensive treatment (yes vs. no)
- Dyslipidemia (untreated and treated)
- Lipid lowering treatment (yes vs. no)
- Diabetes (untreated and treated)
- Treatment of diabetes (yes vs. no)
- Metabolic syndrome (yes vs. no)
- Any cardiovascular disease (TIA, stroke, myocardial infarction, etc.) (yes vs. no)

Race will be modified according to the following rule in order to calculate ethnicity (missing values will be recoded into an appropriate value and if no category can be identified the “Caucasian” group will be assigned)

- Caucasian (1)
- Black (2)
- Asian (3)
- Hispanic (4)

In case of missing value for the following variables the missing value will be recoded to 0:

- Smoking
- Alcohol
- Coffee
- Left ventricular Hypertrophy at the ECG
- Family history for any CV disease
- Hypertension and therapy
- Number of antihypertensive drugs
- Dyslipidemia and therapy

- Diabetes and therapy
- Concomitant diseases and treatments
- Cardiovascular disease
- Cardiovascular risk
- Component of the metabolic syndrome and metabolic syndrome

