### 3.2 EVALUATION OF TARGET ORGAN DAMAGE

#### 3.2.1 CARDIAC DAMAGE

Cardiac damage will be based on LVMI, calculated as LVM divided by BSA, as follows [Devereux RB, Alonso DR, Lutas EM, Gottlieb GJ, Campo E, Sachs I, Reichel N. Echocardiographic assessment of left ventricular hypertrophy: comparison to necropsy findings. Am J Cardiol 1986;57:450-458]:

$$LVM = ( (1.04 * ( ( (IVSD + PWD + LVEDD)^3) / 1000 ) - ( (LVEDD^3) / 1000 ) ) - 3.6 ) / ( (WEIGHT^{0.425}) * (HEIGHT^{0.725}) * 0.007184 ) )$$

Where:

IVSD = Interventricular septal thickness at end-diastole (mm)

PWD = Posterior wall thickness at end-diastole (mm)

LVEDD = LV end-diastolic dimension (mm)

Height is expressed in cm and weight in kg.

LVMI will be recalculated from LVM.

Cardiac damage will be assessed according to ESH guidelines [Mancia G, Fagard R, Narkiewicz K, Redón J, Zanchetti A, Böhm M, Christiaens T, Cifkova R, De Backer G, Dominiczak A, Galderisi M, Grobbee DE, Jaarsma T, Kirchhof P, Kjeldsen SE, Laurent S, Manolis AJ, Nilsson PM, Ruilope LM, Schmieder RE, Sirnes PA, Sleight P, Viigimaa M, Waeber B, Zannad F; Task Force Members. 2013 ESH/ESC Guidelines for the management of arterial hypertension: the Task Force for the management of arterial hypertension of the European Society of Hypertension (ESH) and of the European Society of Cardiology (ESC). J Hypertens. 2013 Jul;31(7):1281-357]:

- Males: LVMI > 115 g/m^2
- Females: LVMI > 95 g/m^2

An attempt will also be made to classify left ventricular hypertrophy according to ECG:

- Sokolow-Lyons index: SV1+RV5-6 >38 mm
- Cornell Index; S in V3 + R in aVL >24 mV in males and > 20 mV in females

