### 3.2 EVALUATION OF THE METABOLIC SYNDROME

The metabolic syndrome will be evaluated according to the harmonized definition [Alberti KG, Eckel RH, Grundy SM, Zimmet PZ, Cleeman JI, Donato KA, Fruchart JC, James WP, Loria CM, Smith SC Jr; International Diabetes Federation Task Force on Epidemiology and Prevention; National Heart, Lung, and Blood Institute; American Heart Association; World Heart Federation; International Atherosclerosis Society; International Association for the Study of Obesity. Harmonizing the metabolic syndrome: a joint interim statement of the International Diabetes Federation Task Force on Epidemiology and Prevention; National Heart, Lung, and Blood Institute; American Heart Association; World Heart Federation; International Atherosclerosis Society; and International Association for the Study of Obesity. Circulation. 2009 Oct 20;120(16):1640-5]. Presence of 3 out of 5 of the following risk factors

a) Elevated waist circumference (Caucasian)

≥94 cm in males  
≥80 cm in females

Elevated waist circumference (South America and Asia)

≥90 cm in males  
≥80 cm in females

When waist circumference is missing a BMI  $\geq 25 \text{ kg/m}^2$  will be used

- b) Elevated triglycerides ( $\geq 150 \text{ mg/dL}$ ) or lipid-lowering treatment
- c) Reduced HDL cholesterol ( $< 40 \text{ mg/dL}$  males and  $< 50 \text{ mg/dL}$  females) or lipid-lowering treatment
- d) Elevated blood pressure ( $\geq 130 / 80 \text{ mmHg}$ ) or antihypertensive treatment
- e) Elevated fasting glucose ( $\geq 100 \text{ mg/dL}$ ) or treatment for diabetes

In case of missing HDL it will be calculated in presence of total cholesterol, LDL cholesterol and triglycerides as

$$\text{HDL} = \text{Total cholesterol} - \text{LDL cholesterol} - \text{Triglycerides} / 5$$

Also Cholesterol LDL and Triglycerides, if missing, will be recalculated starting from the available parameters.

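### The CRF lists do not name the lipid and glucose values that the metabolic-syndrome definition needs, and missing components are recoded to absent, so patients without these values can be wrongly counted as free of the syndrome

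*SAP*

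**What the plan says.** **Data collected.** SAP 2.2 introduces its list with "That CRF must be completed with all the following information". Protocol 14.1 introduces nearly the same list with "The following data will be entered in the e-CRF, for each subject and visit". The only blood or urine values on them are microalbuminuria (the SAP adds "or albumin-creatinine ratio (as mg/g) and serum creatinine") and creatinine. Dyslipidemia and diabetes are each a yes/no item with a note on treatment. Protocol 9.1 uses the 14.1 list as the information required for inclusion, so a patient with no lipid or glucose value is eligible and complete.

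**Definition.** The SAP section on the metabolic syndrome (the second section numbered 3.2) requires "Presence of 3 out of 5 of the following risk factors": (a) waist, (b) triglycerides or lipid-lowering treatment, (c) HDL or lipid-lowering treatment, (d) blood pressure or antihypertensive treatment, (e) fasting glucose or diabetes treatment.

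**Missing data.** SAP 3.1 lists variables whose missing values become 0. The last entry is "Component of the metabolic syndrome and metabolic syndrome".

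**Use.** SAP 3 makes the syndrome one of three main-analysis topics, and SAP 3.1 compares patients with and without it.

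**The concern.** Components b, c and e rest on laboratory values that neither list asks for. Without the value, the component can be met only through a drug. A recorded diagnosis of dyslipidemia or diabetes without treatment earns nothing. The zero-recode rule then treats unknown as absent, so the patient enters the comparison group instead of being left out.

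Two things are at stake. The no group may contain patients who have the syndrome, and the yes/no split may depend largely on drug treatment. SAP 3.1 already compares patients by lipid-lowering and diabetes treatment, so a syndrome comparison that mainly follows the same split would add little.

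**Working it through.** The plan states no prevalence, sample size or power for this comparison, so there is no figure to reproduce. The check applies the SAP's own rule.

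**Inputs.** The 3-of-5 cut and components a to e come from the SAP metabolic-syndrome section, the recoding from SAP 3.1, and the available items from SAP 2.2 and Protocol 14.1. Each indicator below is 0 or 1.

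**Score with laboratory values held:**
S = waist + max(TG, lipid drug) + max(HDL, lipid drug) + BP + max(glucose, diabetes drug)

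**Score with no lipid or glucose value held and missing set to 0:**
S = waist + BP + 2 × (lipid drug) + (diabetes drug)

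**By treatment, no laboratory values:**
- Neither drug: at most 1 + 1 = 2, always a no.
- Diabetes drug only: 1 + waist + BP, a yes only if both waist and BP are met.
- Lipid drug only: 2 + waist + BP, a yes if either is met.
- Both drugs: at least 3, always a yes.

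The BMI substitute for a missing waist replaces component a and does not raise the maximum of 2. The SAP's back-calculation of lipids does not help either: HDL is derived from total cholesterol, LDL and triglycerides, which are also unlisted, and glucose has no counterpart.

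**All 2^7 = 128 profiles** of waist, TG, HDL, BP, glucose, lipid drug and diabetes drug:

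| Treatment | Profiles | Yes, values held | Yes, values not held | Missed |
|---|---|---|---|---|
| Neither | 32 | 16 | 0 | 16 |
| Lipid drug only | 32 | 28 | 24 | 4 |
| Diabetes drug only | 32 | 22 | 8 | 14 |
| Both | 32 | 32 | 32 | 0 |
| Total | 128 | 98 | 64 | 34 |

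No profile becomes a false yes. These are counts of profiles, not proportions of patients.

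**Dependence on treatment.** SAP 2 enrols from hypertensive patients, so BP will be met by most. With BP = 1 and no laboratory values, S = 1 + waist + 2 × (lipid drug) + (diabetes drug). A yes then needs a lipid drug, or a diabetes drug together with a raised waist.

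**Illustrative size.** The prevalences below are assumptions, not from the documents. Factors are taken as independent, and no patient has laboratory values.

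| Assumed prevalence | Low | Middle | High |
|---|---|---|---|
| Waist | 50% | 60% | 70% |
| BP | 90% | 95% | 100% |
| TG; HDL (each) | 20% | 30% | 40% |
| Glucose | 20% | 35% | 50% |
| Lipid drug | 20% | 30% | 40% |
| Diabetes drug | 5% | 10% | 15% |
| **Result** | | | |
| True syndrome | 42.4% | 65.7% | 83.4% |
| Classed yes | 20.9% | 33.4% | 46.3% |
| Sensitivity | 49.1% | 50.9% | 55.5% |
| Share of no group with the syndrome | 27.3% | 48.5% | 69.1% |

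The last row is (true − classed) / (1 − classed); for the low case, (0.424 − 0.209) / (1 − 0.209) ≈ 0.27. If missed patients had the same mean BP or PWV as detected ones, the observed yes-minus-no difference would be (1 − share) of the true one, about 73% down to 31%. Missed patients are mostly untreated, so that condition may fail, and the direction of bias in the difference is not fixed.

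**The case against.** The strongest reply is that the values may well be collected. Neither list is said to be exhaustive. The protocol synopsis and section 10.1 say the e-CRF will take laboratory tests in general. Protocol 14.1 has no item for outcome events, although section 11 analyses them and SAP 2.2 mentions an events section, so 14.1 is not the whole e-CRF. The SAP's back-calculation of missing lipids makes sense only if some lipid fields exist.

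This stands as far as it goes. A reader might infer that lipids and glucose are not collected and that the main comparison is therefore misclassified. The documents do not support that: they do not show the e-CRF build, and the syndrome is one of three main topics, one of 19 groupings in SAP 3.1, and in none of the protocol objectives. Nor do the groups simply become treated versus untreated. Treatment is necessary for a yes when no values are held, but it is not sufficient. That BP plus a lipid drug reaches 3 is the SAP definition itself and holds with complete data too.

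The reply does not remove the defect. A general reference to laboratory tests names and requires no analyte. If the fields are optional, each blank still counts as absent. For example, a patient on neither drug, with raised waist, BP met, normal lipids and no glucose value, scores 2 and becomes a no, although the true status is unknown.

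**Conclusion.** The point holds in conditional form. The values needed for three of five components are not named in either list, and the zero-recode rule turns each unknown into an absence. For patients with none of these values and on no lipid or diabetes drug, sensitivity is 0% by construction, as a worst case. Classification errors run only towards no. The extent across the registry cannot be derived from the documents; the 49–56% sensitivity and 27–69% contamination rest on assumed, independent prevalences and on nobody having laboratory values. The change should be made before the syndrome analysis is run.

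A secondary gap is similar but weaker. SAP 3.2.1 recalculates LVMI from septal thickness, posterior wall thickness and cavity dimension, while the lists name only LVMI. Cardiac damage can still be classified, because the cut-offs of 115 and 95 g/m² apply to the reported LVMI. What is not secured is one uniform calculation across centres.

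**What to change.** 1. In Protocol 14.1 and SAP 2.2, name triglycerides, HDL, LDL, total cholesterol and fasting glucose, with units and date, to be entered whenever the routine record holds them. If the e-CRF already has these fields, say so. No test is added, in keeping with Protocol 12.3.
2. Remove the metabolic syndrome and its components from the zero-recode list in SAP 3.1.
3. Class a patient as yes with at least three components known present, and as no with at least three known absent (at most two can then be present). Otherwise class the patient as undetermined and leave that patient out of the yes/no comparison. Judge known absence on values before recoding, because the lipid, diabetes and hypertension therapy items are on the same zero-recode list.
4. Report the number undetermined, by centre and treatment, and add a sensitivity analysis such as multiple imputation of the missing components.
5. Add the three echocardiographic dimensions where available; otherwise use the reported LVMI and flag its source.

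The cost is more data entry, a smaller analysis set, and possible selection towards patients with laboratory values, which item 4 is meant to expose. Items 2 and 3 need no new data.

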### 3. ANALYSIS

The main analysis will assess:

- The general clinical characteristics of the population
- The relationship between BP and arterial stiffness and target organ damage / cardiovascular events
- The features of BP and arterial stiffness in presence of the metabolic syndrome

The following inclusion criteria will be considered:

- Male and female aged  $\geq 18$  years
- Good quality ABPM: i) at least 70% of the number of the expected readings over the 24 hours (discarded), ii) at least 20 valid measurements during the daytime and 7 during the nighttime

The parameters assessed will be:

- 24-hour average brachial SBP and DBP
- 24-hour average aortic SBP and DBP
- 24-hour average PWV
- 24-hour average aortic AI

- 24-hour wSD of SBP and DBP
- 24-hour ARV of SBP and DBP

Analysis will be done also for the day-time and night-time subperiods.

In each individual PWV will be normalized to a SBP of 100 mmHg and a HR of 60 bpm by a regression analysis of 24-hour PWV to 24-hour SBP and 24-hour HR. AI will be normalized to a HR of 75 bpm with the same procedure.

Statistical tests to be used will include analysis of variance (ANOVA) or covariance (ANCOVA) for continuous variables with adjustments for confounding factors. Discrete variables will be analyzed by Chi-square test or logistic regression analysis. Survival analysis will be carried out by Kaplan-Meier plots, log rank test and Cox regression.

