4.0 SYNOPSIS

Project title	INTERNATIONAL REGISTRY FOR AMBULATORY BLOOD PRESSURE AND ARTERIAL STIFFNESS TELEMONITORING
Project name	VASOTENS (Vascular health ASsessment Of The hypertENSive patients) REGISTRY
Scientific Coordinator	[name] (Italy) Clinical Research Unit Italian Institute of Telemedicine [name] Italy
Co-coordinator	[name] (Russia) [name] Hemodynamic Laboratory Nizhniy Novgorod Russia
Project centers	At least 30 Hypertension centers will be involved in the project, each one providing at least 100 patients, which will be followed-up over time. Centers will be selected in different countries, initially in Europe, starting from Italy and Russia. Mandatory criteria of a center to be included in the study are the availability in the facility of a BPLab ABPM monitor, the potential for providing and properly following-up the number of patients required by the protocol, the availability of Internet connection, regular access to the web and human resources to upload ABPM and clinical data.
Date of starting of the project	Launch of the project (first investigators' meeting): June 2015 First patient uploaded into the database: September 2015

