10.3 Dissemination activities

An important part of activities in this project will be aimed at disseminating the knowledge on correct use of ambulatory blood pressure and arterial stiffness estimation in clinical practice and in research and thus at achieving a possibly standardized and widespread use of this integrated technology in the participating centers. In order to achieve these aims the project, apart from data collection, will involve the following activities:

- Exchange of knowledge between participating centers already expert in ABPM use and in arterial stiffness measurement. This will be mainly achieved by cooperation of investigators in preparing a possibly unified methodology of ABPM data collection and analysis and by jointly addressing methodological issues that may arise during the project.
- Performance of studies aimed at optimizing a possible clinical application of non-invasive ambulatory arterial stiffness estimation, based on data collected in the Registry
- Providing instructions on appropriate ambulatory arterial stiffness monitoring methodology to other physicians. Indeed, an important feature of the project will be to actively involve intermediate level centers, not necessarily expert in ABPM use and arterial stiffness determination. A major task of the consortium will be to provide these participants with an accurate information on correct methodology and interpretation of such data, in order to support them in case of difficulties and to monitor the correctness of the use of the methodology in these centers during the project
- Preparation of specific recommendations on the use and clinical application of ABPM integrated with arterial stiffness evaluation
- Cooperation with international and national scientific societies in the area related to ABPM and arterial stiffness monitoring. The majority of the VASOTENS Scientific Committee members will be selected among active members of international and national hypertension societies, including the membership in the bodies specifically dedicated to blood pressure and arterial stiffness measurement. This will facilitate the dissemination of information on the project and its findings and will also allow an interaction with writing committees involved in the preparation of guidelines pertinent to this area

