## 2. DATA COLLECTION

Detailed study procedures and further information and details on the study are available in the study protocol.

Briefly, each center will enroll 100 patients from their pool of hypertensive patients. There are no specific inclusion criteria, except that:

- Patients must be at least 18 years-old
- Patients with frequent ectopic beats, including atrial fibrillation must be excluded
- Arm circumference must be at least 22 cm (appropriate cuff must be used in case of large arms)

Patients will be visited ideally at 6 month-intervals or once-a-year. During the visit they will be submitted to an ABPM and clinical data (see below) will be collected.

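### The SAP gives centre and country no role in the planned tests, so results may be too optimistic or confounded where exposure and outcome both vary by centre

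*SAP*

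**What the plan says.** **Design.** Protocol section 4.0 plans: "At least 30 Hypertension centers will be involved in the project, each one providing at least 100 patients". SAP section 2 states that "each center will enroll 100 patients from their pool of hypertensive patients". Neither document gives a total; 30 × 100 = 3,000 is a derived minimum. Recruitment begins in Italy and Russia, and other countries may join (Protocol sections 9.0 and 12.3).

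**Tests.** SAP section 3 lists three families:
- Continuous variables: "Statistical tests to be used will include analysis of variance (ANOVA) or covariance (ANCOVA"), "for continuous variables with adjustments for confounding factors". The factors are not named.
- Discrete variables: "Discrete variables will be analyzed by Chi-square test or logistic regression analysis".
- Events: "Survival analysis will be carried out by Kaplan-Meier plots, log rank test and Cox regression".

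Protocol section 11.0 adds that the Cox model will be used to study predictors of outcome. Neither document mentions centre or country in connection with any analysis.

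**Signs that centres may differ.** Protocol section 10.3 intends to "actively involve intermediate level centers, not necessarily expert in ABPM use". Data already held by centres are pooled with new subjects (Protocol section 9.0). The aortic-length surrogate is a manual distance entered when the device is programmed (SAP section 2.1). The office pressure may be an average or a single reading (SAP section 2.2). Investigators transcribe laboratory and instrumental results themselves (Protocol section 14.1), and no central reading of LVMI or IMT is described.

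**The concern.** As named, these tests treat all patients as independent. Patients of one centre share operators, equipment, referral patterns and recording habits. Two separate problems can follow.

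- **Precision.** If a factor and an outcome both cluster by centre, the pooled standard error understates the true uncertainty. Candidates in SAP section 3.1 are ethnicity, treatment status, alcohol and comorbidity. The recoding rule there can add to the clustering: a blank becomes 0, and unidentifiable ethnicity becomes Caucasian, so a centre that under-records an item moves its patients into one category together.
- **Bias.** If the centres that record higher stiffness also tend to record higher (or lower) LVMI or IMT, a pooled analysis can create or hide an association that does not exist within centres.

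This touches one of the three stated aims of the main analysis in SAP section 3: the relation of blood pressure and stiffness to target organ damage and cardiovascular events.

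**Working it through.** The plan has no sample-size calculation, alpha or ICC, so there is no figure of its own to reproduce. The check asks how far a test that ignores centre departs from its nominal 5% level.

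**Inputs.** From the documents: k = 30 centres and m = 100 patients per centre, both minima. Assumed: the centre ICC of the outcome (ρy) and of the factor (ρx).

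**Formulas**, for a comparison of means or a linear slope:
- Design effect: DE = 1 + (m − 1) × ρx × ρy
- True SE ÷ pooled SE = √DE
- Actual type I error = 2 × [1 − Φ(1.96/√DE)]
- Effective sample size = 3,000/DE

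Example with both ICCs 0.05: DE = 1 + 99 × 0.05 × 0.05 = 1.25; √DE = 1.12; type I error = 7.9%; effective size = 2,405.

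| ρy | ρx | DE | SE ratio | Type I error, formula | Simulated, centre ignored | Simulated, centre fixed effects |
|---|---|---|---|---|---|---|
| 0.05 | 0 | 1.00 | 1.00 | 5.0% | 4.7% | 5.0% |
| 0.05 | 0.05 | 1.25 | 1.12 | 7.9% | 8.2% | 5.0% |
| 0.05 | 0.10 | 1.50 | 1.22 | 10.9% | 10.0% | 4.2% |
| 0.10 | 0.10 | 1.99 | 1.41 | 16.5% | 16.2% | 4.5% |
| 0.05 | 0.30 | 2.49 | 1.58 | 21.4% | 21.2% | 5.2% |

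The simulations used 30 centres of 100, a true slope of zero and 2,000 replicates per row.

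**Balanced factor.** If a factor is split equally within every centre, ρx = −1/99. Then DE = 0.95 for ρy = 0.05 and 0.90 for ρy = 0.10. The formula gives 4.4% and 3.9%; simulation gave 4.7% and 3.9%. The pooled test is slightly conservative.

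**Extreme bound.** For a purely centre-level factor (ρx = 1) with ρy from 0.02 to 0.10, DE runs from 2.98 to 10.9 and type I error from 26% to 55%.

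**Confounding.** Suppose the centre effects on exposure and outcome also correlate at 0.5 (assumed). The expected pooled slope is then about 0.5 × √(ρx × ρy) instead of zero.
- Both ICCs 0.05: about 0.025 in SD units. Simulated bias 0.023, with 28% false positives.
- Both ICCs 0.10: about 0.050. Simulated bias 0.048, with 67% false positives.

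With centre fixed effects, the mean slope stayed within about 0.001 of zero and rejection was 5.6–5.7% in these two cases. Across all scenarios run with fixed effects, rejection was 4.2–5.7%.

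**The case against.** A reader might infer that the plan's standard errors are too small throughout and that centre does confound the organ-damage results. The documents do not support that. Underestimated standard errors require both factor and outcome to cluster by centre. Confounding further requires their centre effects to be correlated. The documents contain no ICC and no centre-level data, and a comparison such as sex, if balanced within centres, would be unaffected.

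Nor does the plan exclude centre. Its list of tests is worded as open-ended, covariate adjustment is foreseen, and logistic and Cox models accept covariates. Protocol section 19.0 sends each proposed analysis through a separately approved plan. The registry also takes steps that should reduce centre variation: one make of device, central data collection with expert validation (Protocol section 10.1), a quality check before stiffness measures are calculated (section 10.2), training and oversight of less expert centres (section 10.3), and one formula for LVMI (SAP section 3.2.1). The passage on less expert centres concerns ambulatory monitoring and stiffness, not echocardiography or carotid ultrasound. Local reading of LVMI and IMT is an inference from the transcription rule, not a stated fact.

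The upper range of 26–55% needs a factor fixed by centre. Every grouping in SAP section 3.1 is a patient characteristic, as are stiffness and blood pressure. The formula is also for means, and its transfer to log-rank and Cox was not tested.

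All of this limits the size of the point; the gap remains. The adjustment wording names no factor and is attached to continuous variables only. Plain chi-square and log-rank tests have no place for centre unless stratified. An open-ended list permits a better method but does not commit to one.

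**Conclusion.** The point holds in conditional form. It is certain that neither document says how centre or country will be handled in a design of at least 30 centres with at least 100 patients each. The consequence depends on ICCs that the documents do not give. With 100 per centre and a test of means, type I error is about 8% with both ICCs 0.05, about 11% with outcome 0.05 and factor 0.10, about 16% with both 0.10, and about 21% with outcome 0.05 and factor 0.30. It stays near or slightly below 5% for factors balanced within centres. The 26–55% range is only an extreme bound. Confounding by centre is a plausible risk, given manual aortic-length measurement, transcribed organ-damage results, pooled existing databases and mixed expertise, but it is not established. The SAP should be amended: the omission affects a main analysis, and the data needed for the remedy are already held.

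**What to change.** In SAP section 3, name the confounders and state how centre enters each analysis:
- **ANCOVA and logistic models:** centre as fixed effects, or a random intercept for centre plus the centre mean of the exposure. A random intercept alone does not fully remove confounding by centre.
- **Cox and log-rank:** stratify by centre, or by country if events per centre are sparse. Stratifying by country leaves differences between centres within a country uncontrolled.
- **Chi-square:** replace it with a Cochran-Mantel-Haenszel test stratified by centre, or use the centre-adjusted logistic model.
- **Cluster-robust errors, if used:** apply a small-sample correction for about 30 clusters. They correct the variance only, not confounding.
- **Reporting:** give the estimated ICCs of the main stiffness and organ-damage variables.

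**Cost.** The change needs SAP text and standard software. SAP section 1 already builds the centre code into each investigator's identifier, so no new data are needed. Some intervals will widen, purely between-centre contrasts lose precision (with centre fixed effects they cannot be estimated), and centres without events contribute nothing to a centre-stratified Cox model.
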